# 8.3.1. Patient characteristics

- 1. Enter the information at the start of administration of this drug into the registration form
  - ID number
  - Gender

- Birth year and month/age (if birth year and month cannot be disclosed, age at the start of administration of this drug)
- Start date of treatment with this drug
- Eligibility
- 2. The following will be recorded in CRF at the start of administration of this drug:

(ID number, gender, and birth year and month/age in the Registration Form are automatically reflected in the CRF. The investigators should check and update the CRF as needed.

- ID number
- Gender
- Birth year and month/age
- Height (cm)
- Weight (kg)
- History of smoking
- Presence/absence of symptoms of the target disease (disease for which this drug is used), severity, and date of onset

The presence/absence of symptoms will be judged based on the clinical symptoms related to infections caused by SARS-CoV-2, including but not limited to the symptoms shown below.

Cough, shortness of breath or dyspnea, feeling hot, chills or shivering, fatigue (decreased energy or feeling tired), muscle pain or body pain, diarrhea (loose or watery stools), nausea (queasy), vomiting, headache, sore throat, stuffy or runny nose, dysosmia, dysgeusia, and findings of pneumonia

Severity should follow the severity classification in the "Clinical Practice Guidance for New Coronavirus Infection COVID-19" (see Table 2).

**Table 2.** Severity classification

Severity	Oxygen saturation	Clinical status
Mild	SpO 2 ≥96%	No respiratory symptoms, or cough alone with no dyspnea
		No finding of pneumonia in either case
Moderate I	93% <spo2<96%</spo	Dyspnea, pneumonia findings
No respiratory failure	9370\SpO 2 \9070	Dyspica, pileumonia midnigs
Moderate II		
Respiratory failure	SpO 2 ≤93%	Oxygen required
present	_	
Severe		Admitted to ICU or requiring mechanical
Severe		ventilation

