### **8.3.7.2.** Vital signs

Results of tests performed before administration (including the start date of administration) and during observation period should be recorded.

- 1. Date of tests
- 2. Items of tests
  - Body temperature and percutaneous arterial oxygen saturation (SpO2)

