- History of use of drugs for the treatment of infection caused by SARS-CoV-2 [history of use absent, history of use present, unknown]
- Number of days from the onset of symptoms of infection caused by SARS-CoV-2 to the start of treatment with this drug [within 3 days, 4 or 5 days, 6 days or more, unknown] If the onset of symptoms and the start of treatment with this drug are on the same day, the number of days will be 0.
- Symptoms and severity of infection caused by SARS-CoV-2 at the start of treatment with this drug [no symptoms, mild, moderate I, moderate II, severe, symptoms or severity unknown]
- Number of risk factors for aggravation of infection caused by SARS-CoV-2 [none, 1, 2, 3, 4, number unknown, unknown]. If there are risk factors but the number is unknown, the patient will be classified as "number unknown." If it is not known that there are risk factors, the patient will be classified as "unknown."
- SARS-CoV-2 vaccination history [present, absent, unknown]
- Number of SARS-CoV-2 vaccination doses (vaccination on or before the day before the start of treatment with this drug) [none, 1, 2, 3, 4 or more, unknown]
- Hepatic impairment [absent, present, unknown]

- Hepatic impairment [absent, mild, moderate, severe, unknown (presence unknown or severity unknown)]
- Renal impairment [absent, present, unknown]
- Renal impairment [absent, mild, moderate, severe, unknown (presence unknown or severity unknown)]
- Age [<15 years, ≥15 years]
- Age [<65 years, ≥65 years]
- Pregnancy [absent, present] * Female only

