7. HANDLING OF MISSING DATA

If the seriousness, causal relationship, treatment, and outcome of an adverse event are missing, the data will be handled as "unknown" for tabulation.

If there are no measured values within the acceptable window for each time point of evaluation of efficacy endpoints (Appendix 2), the values will be handled as missing and will not be imputed. Definitions of acceptable windows for other endpoints are provided in Appendix 2.

If the date of admission is missing or partial, the last complete date among the following will be used as the imputed date.

- Start date of this drug
- The first day of the month of the same month as the date of admission (if the day of admission is missing and the month and year are available)
- The first day of the year of the same year as the date of admission (if the month and day of admission are missing and the year is available)

If the date of death and the date of last observation are missing or partial, the latest complete date among the following will be used as the imputed date.

- Start date/end date of this drug
- Start date/end date of concomitant drug therapy
- Start date/end date of concomitant non-drug therapy
- Viral test
- Date of measurement of body temperature/SpO₂
- Date of admission/date of discharge
- Date of efficacy evaluation (date of the highest severity/date of evaluation at the end of the observation period)
- Date of onset of adverse event, resolution/recovery of adverse event, date of death
- The first day of the month of the same month as the date of last observation (if the day of last observation is missing and the month and year are available)
- The first day of the year of the same year as the date of last observation (if the month and day of last observation are missing and the year is available)

The policy for handling uncleaned data is described below.

- Items of missing data: Values will be handled as missing (category of categorical variables is "not recorded") in both tabulation and listing.
- Items of inconsistent data: Inconsistent data will be handled as missing in both tabulation and listing. However, a list of data handling will be prepared separately.
- No signature: The descriptions in the CRF without the signature of the contract physician (including the case of only the signature of a physician other than the contract physician) will be handled as missing in both tabulation and listing.

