- SARS-CoV-2 viral load (continuous) before the start of treatment with this drug (including the start date of treatment)
- SARS-CoV-2 viral load before the start of treatment with this drug (including the start date of treatment) [≥4 log₁₀ copies/mL, <4 log₁₀ copies/mL, unknown] [≥7 log₁₀ copies/mL, <7 log₁₀ copies/mL, unknown]
- SARS-CoV-2 variant before the start of treatment with this drug (including the start date of treatment) (wild strain, Beta variant, Gamma variant, Delta variant, Omicron variant, unknown)
- Percutaneous arterial oxygen saturation (SpO₂) before the start of treatment with this drug (including the start date of treatment) [\geq 96%, \geq 93% to \leq 96%, \leq 93%, unknown]
- Percutaneous arterial oxygen saturation (SpO₂) before the start of treatment with this drug (including the start date of treatment) [≥95%, <95%, unknown]

• Findings of pneumonia due to infection caused by SARS-CoV-2 at the start of treatment with this drug [absent, present, unknown]

- Administration of oxygen for infection caused by SARS-CoV-2 performed since before the start of treatment with this drug [present]
- Artificial ventilation with intubation for infection caused by SARS-CoV-2 performed since before the start of treatment with this drug [present]
- ECMO for infection caused by SARS-CoV-2 performed since before the start of treatment with this drug [present]

Using the safety analysis set, the following aspects of patients will be summarized in terms of number and proportion by system organ class (SOC) and by preferred term (PT):

- Breakdown of medical history
- Breakdown of complications
- Breakdown of complications (those corresponding to risk factors for aggravation of infection caused by SARS-CoV-2)

In the safety analysis set, Efficacy Analysis Set 1, Efficacy Analysis Set 2, and Efficacy Analysis Set 3, the following number and proportion of patients will be tabulated. All the therapies used between the start date of treatment with this drug and Day 28 after the end of treatment will be included.

- Breakdown of concomitant drug therapies (those other than SARS-CoV-2 vaccines whose reason for use is infection caused by SARS-CoV-2) [remdesivir (Veklury), molnupiravir (Lagevrio), dexamethasone, baricitinib (Olumiant), casirivimab/imdevimab (Ronapreve), sotrovimab (Xevudy), tocilizumab (Actemra), tixagevimab/cilgavimab (Evusheld), ensitrelvir fumarate (Xocova), other]

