8.2.4.8. Exploratory analyses

For Efficacy Analysis Set 1, changes over time in viral load, body temperature, and percutaneous arterial oxygen saturation (SpO₂) in individual patients will be superimposed on the figures. For measured values before the start of treatment with this drug (including the start date of treatment), the last measured value before the start of treatment with this drug will be shown based on the handling of each endpoint in Section 6.3.

Additional analyses may be performed as necessary. Exploratory analyses will be reported only if results provide important interpretation.

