10.2. Appendix 2: Data Extraction Details

 Table 2.
 Definitions of Acceptable Windows for Timing

Timing	Endpoint	Definition [acceptable window]
At the start of treatment	Efficacy endpoints, viral load, body temperature, percutaneous arterial oxygen saturation	From 30 days prior to the date of first dose in this study (start date of treatment) to the start date of treatment
During the observation period	Safety endpoints, efficacy endpoints, viral load, body temperature, percutaneous arterial oxygen saturation, concomitant drug therapy, and non-drug therapy	Start date of treatment to Day 28 after the end of treatment
End date of the observation	Efficacy endpoints	Primary definition: Up to Day 28 after the end of treatment
period		Secondary definition 1: Up to 42 days after the end of treatment
		Secondary definition 2: Entire period

10.3. Appendix 3: Data Entries Related to Efficacy Endpoints and Their Handling, and Assessment of Endpoints

Table 3. Worsening of Severity and Highest Severity of Infection Caused by SARS-CoV-2

Symptoms	Severity at			Worsening of	of severity: H	ighest sev	erity			
at the start of	the start of treatment	Worsening	Vorsening of severity during the observation period							
treatment	with this	Absent		Present						
with this	drug	Highest seve	erity	ity						
drug		NA	Mild	Moderate I	Moderate II	Severe	Unknown	NA		
Absent	NA	Absent: NA	Present: Mild	Present: Moderate I	Present: Moderate II	Present: Severe	Present: Unknown	Unknown: NA		
Present	Mild		Case 1				Case 2			
	Moderate I									
	Moderate II									
	Severe	Severe at the start: NA	Case 3							
	Unknown	Absent: NA	Case 4							
Unknown	NA	Case 5								

NA: not applicable

Discrepancies between evaluations at the start of treatment with this drug and during the observation period are subject to re-investigation, but the reasons for being subject to re-investigation and handling of cases where there is no change as a result of re-investigation are shown below.

- Case 1: Assessed as "Unknown: NA" because the highest severity is lower than the severity at the start of treatment with this drug.

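### SAP Table 2 accepts viral load, body temperature and SpO2 from up to 30 days before the first dose as baseline, without requiring that they belong to the current infection

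*SAP*

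**What the plan says.** SAP Appendix 2, Table 2 has one row for the start of treatment. It covers "Efficacy endpoints, viral load, body temperature, percutaneous arterial oxygen saturation", and its window runs "From 30 days prior to the date of first dose in this study (start date of treatment) to the start date of treatment". SAP Section 7 states, for efficacy endpoints, that where no value lies in the window "the values will be handled as missing and will not be imputed". It refers the other endpoints to the same appendix for their windows.

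The protocol sets no narrower limit at collection. Section 8.3.7.2 on vital signs says "Results of tests performed before administration (including the start date of administration) and during observation period should be recorded", and Section 8.3.7.1 says the same of viral tests. Neither mentions symptom onset or the current episode.

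Baseline SpO2 and viral load are summarised in SAP Section 8.2.2.1, in categories that include an unknown level, and viral load also as a continuous variable. Baseline temperature is not summarised there. In the individual-patient figures of SAP Section 8.2.4.8, "the last measured value before the start of treatment with this drug will be shown". SAP Section 6.3 adds only a same-day rule: the higher temperature and the lower SpO2.

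SAP Section 5.4 grades the time from symptom onset to first dose as "within 3 days, 4 or 5 days, 6 days or more, unknown".

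**The concern.** The SAP treats this as an illness that moves in days, yet allows a month for measurements that change within days. A patient with no SpO2 or viral load recorded during the illness, but with a value from an unrelated visit two or three weeks before, is not classed as unknown. The old value is accepted as the start-of-treatment value.

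The study is well placed to produce such cases. Data are transcribed from routine records and may be missing (Protocol 8.4 and 8.9). The notes to the protocol's severity table call SpO2 measurement desirable, not required. SAP Section 8.2.2.1 itself expects patients with an earlier SARS-CoV-2 infection, and patients already in hospital for other reasons.

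At stake are the SpO2 and viral load rows of the baseline table, and the starting points of the individual plots. In a plot, the step from a pre-illness value to an in-illness value would look like a change after the drug was started, and a single-arm study has no control group to show otherwise.

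**Working it through.** The plan gives no figure that depends on this window, so there is nothing to reproduce. The check is a count of dates, followed by an illustration of size.

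**1. Dates accepted before symptom onset.** The window runs from day -30 to day 0, which is 31 dates. With onset d days before the first dose, 30 - d of them precede onset. The documents give no incubation period. Assuming i = 0 to 14 days, 30 - d - i dates precede infection.

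| Onset before first dose (d) | Dates before onset | Dates before infection, i = 0 to 14 (assumed) | Dates from onset to first dose |
|---|---|---|---|
| 0 days | 30 | 30 to 16 | 1 |
| 3 days | 27 | 27 to 13 | 4 |
| 5 days | 25 | 25 to 11 | 6 |
| 6 days | 24 | 24 to 10 | 7 |

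For anyone treated within 5 days of onset, at least 11 of the 31 accepted dates precede infection, even with 14 days' incubation.

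**2. Whether another rule closes the gap.**
- Collection (Protocol 8.3.7.1 and 8.3.7.2): no lower date limit.
- Baseline table (SAP 8.2.2.1): limited to values up to and including the start date, with no lower limit of its own and no rule for choosing among several values. If Table 2 did not govern these rows, they would have no lower limit at all.
- Figures (SAP 8.2.4.8): the last-value rule prefers the most recent measurement, so an old value is plotted only when nothing later was recorded before treatment. The rule is written for the figures only.

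**3. Which results use the window.** Baseline symptoms and severity are entered by the investigator: "The following will be recorded in CRF at the start of administration of this drug" (Protocol 8.3.1). Worsening, resolution and improvement are derived from those entries and the follow-up entries (SAP 6.2 and Tables 3 to 5). Death comes from adverse event outcomes, and hospitalization from the hospitalization record. None is computed from the SpO2, temperature or viral load series, and none of the three is a subgroup factor in SAP 5.4.

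**4. Illustration only.** Let s be the share of the cohort whose only recorded baseline SpO2 predates the illness. Assume that 15% of in-illness values and 2% of pre-illness values are below 96%. The table then shows (1 - s) x 15% + s x 2%:
- s = 5%: 14.25% + 0.10% = 14.35%
- s = 10%: 13.5% + 0.2% = 13.7%
- s = 20%: 12.0% + 0.4% = 12.4%

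With those patients classed as unknown, the whole-cohort row would read 14.25%, 13.5% and 12.0%, with 5%, 10% and 20% shown as unknown. Among patients with a known value it would read 15% in each case. None of these inputs is in the documents.

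**The case against.** The strongest reply is that very little depends on this. No endpoint uses these series, the study is declared non-confirmatory (SAP Section 4), and the baseline table also reports symptoms, physician-graded severity, pneumonia findings, and oxygen, ventilation and ECMO before treatment. A stale value enters only if two things coincide: no in-illness measurement was recorded, and a pre-illness one within 30 days was. Test dates are collected and listings of viral tests, temperature and SpO2 are planned (SAP Section 9), so old values can be traced. All of this stands, and it sets the weight of the point.

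Three stronger readings should be resisted.
- A reader might infer from the words on efficacy endpoints in the Table 2 row that worsening or improvement is measured against stale baselines. The protocol has symptoms and severity recorded at the start of administration, so the documents do not support that.
- A reader might equate the share lacking an in-illness value with the share carrying an old one. Patients with neither are already unknown, so the second share is at most the first, and the documents give neither.
- A reader might conclude that the cohort will look healthier than it was. For SpO2 that is plausible in affected patients. For viral load it is not established, since a result from another episode could be high.

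It is also fair to object that a bound at symptom onset alone would discard valid tests of the same infection taken before symptoms. The fix allows for this.

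**Conclusion.** The point holds as a minor, inexpensive correction. Table 2 is the only lower bound on start-of-treatment viral load, temperature and SpO2, and it lets a pre-illness value stand where the SAP's own unknown category belongs. The effect is limited to the SpO2 and viral load rows of SAP 8.2.2.1 and the individual plots of SAP 8.2.4.8.

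The date count is firm as to symptom onset. Its extension to infection rests on the assumed incubation of 0 to 14 days. The number of patients affected cannot be derived. As the illustration shows, the gain lies in labelling unknown baselines honestly: the whole-cohort proportion below 96% hardly moves, and 15% is recovered only among patients with a known value.

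**What to change.** In Table 2, give viral load, body temperature and SpO2 their own start-of-treatment row:
- The lower bound is the earlier of the recorded symptom-onset date and the first positive test of this episode, never earlier than the present 30 days. The SAP should say how a test is assigned to this episode.
- If neither date is known, a short window fixed in advance applies.
- The last value on or before the start date is used in the SAP 8.2.2.1 summaries as well as in the figures, with the existing same-day rule for temperature and SpO2.
- Patients without such a value are classed as unknown.

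The onset and test dates are already collected, so no new data are needed. The cost is a short edit and a few more unknown baselines. The SAP's revision history marks version 5 as completed. If the tables have already been run, a documented re-tabulation of these rows and plots would serve.

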# 8.2.3.1. Site requirements

Sites where patients can be followed up at the time of the site visit or by telephone, home visit, etc. after administration of this drug.

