#### 8.2.6. Observation period

From the start date of administration to 28 days after the completion of administration (The day after the completion of administration is Day 1.)

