#### 8.3.8. End-of-study / Discontinuation record

The end date of the observation period (date of medical examination on or after Day 28 after the completion of administration) should be recorded. If the patient cannot be followed up until Day 28 after the completion of administration (including Day 28), record date of discontinuation and select only one of the following items that corresponds to the primary reason. If the primary reason corresponds to patient death, necessary information should be recorded in the adverse event field.

- 1. End date of the observation period (date of examination on or after Day 28 after the completion of administration or date of discontinuation)
- Status at the end
  - Completed
  - Symptoms improved
  - Death

- Transferred to other hospital
- Lost to follow-up
- Other

However, if the patient does not return for follow-up visit after the start of administration (including confirmation by telephone, etc.), the information should be recorded in the "lost to follow-up."

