# 8.3.9. Effectiveness evaluation (severity)

The presence/absence of worsening of the severity of infections caused by SARS-CoV-2 after administration of this drug during the observation period (until Day 28 after the completion of administration [including Day 28]), highest severity, and presence/absence and severity of symptoms on the end date of the observation period (date of medical examination on or after Day 28 after the completion of administration) should be entered. For cases discontinuing observation in less than 28 days after the completion of administration, the highest severity by that point and the severity as of the date of discontinuation of the observation period should be recorded (see Table 2 for severity).

- 1. Worsening of severity after administration
  - Presence/absence of worsening of symptoms
  - Date of highest severity
  - Highest severity
- 2. Severity on the end date of the observation period
  - Date of evaluation
  - Presence/absence of symptoms of infections caused by SARS-CoV-2
  - Severity

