# • Analysis for effectiveness evaluation

For Effectiveness Analysis Sets 1, 2, and 3, the number of patients by highest severity after administration of this drug and the number of patients by severity on the end date of the observation period will be tabulated.

For Effectiveness Analysis Set 1, the number of patients who died for any reason during the period from the start date of administration to Day 28 will be tabulated.

For Effectiveness Analysis Sets 2 and 3, the number of patients who have been hospitalized for treatment of infections caused by SARS-CoV-2 or died for any cause during the period from the start date of administration to Day 28 will be tabulated. The number of respective patients will also be tabulated. The number of these patients will also be tabulated in the subgroup of patients with no history of treatment with drugs for infections caused by SARS-CoV-2.

Detailed methodology for summary and statistical analyses of the data collected in this study will be documented in the SAP, which will be dated and retained by Pfizer. The SAP may modify the plans outlined in the full protocol; however, any significant modifications of definitions or analyses of endpoints will also be reflected in a protocol amendment.

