6.2. Efficacy Endpoints

Unless otherwise specified, the efficacy evaluation period will be the observation period in Section 2.2. The number of days from the start date of treatment to the onset date of event will be calculated as [event onset date – start date of treatment with this drug + 1]. In the analyses related to the end date of the observation period, the primary definition of the end date will be up to Day 28 after the end of treatment, and the secondary definition will also be defined for evaluation (Section 10.2 Table 2).

The following efficacy endpoints are defined for Efficacy Analysis Sets 1, 2, and 3.

• Worsening of severity of infection caused by SARS-CoV-2: Whether the severity of infection caused by SARS-CoV-2 has worsened will be evaluated. However, when the severity is severe at the start of this drug and does not worsen during the observation period, it will be considered as "severe at the start of treatment." Otherwise, if the date of the highest severity is the day after the end of the evaluation period or later, it will be handled as "unknown (highest severity recorded after the end of evaluation period)." Therefore, the categories will be as follows. "Worsened" will be considered as an

event. The expected entries in the CRF and their handling, and assessment of endpoints are shown in Section 10.3 Table 3.

- Not worsened, worsened, severe at the start of treatment, unknown (highest severity recorded after the end of the evaluation period, worsening unknown, no record of worsening)
- Highest severity: The highest severity will be evaluated for patients with the above worsening of severity of infection caused by SARS-CoV-2. If the highest severity is unknown but the severity is considered to have worsened, the highest severity will be "moderate II or severe (indistinguishable)" for patients with the initial severity of moderate I and as "severe" for patients with the initial severity of moderate II. It consists of the following categories. The expected entries in the CRF and their handling, and assessment of endpoints are shown in Section 10.3 Table 3.
 - Mild, moderate I, moderate II, severe, moderate II or severe (indistinguishable), unknown (severity unknown, severity not recorded)

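### The SAP's primary window for end-date outcomes closes on Day 28, the first day on which the protocol lets a completer be examined, so completers seen later are counted as unknown

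*SAP*

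**What the plan says.** Protocol 8.2.6 sets the observation period as "From the start date of administration to 28 days after the completion of administration". The evaluation at its end may come later. Protocol 8.3.8 asks for the "End date of the observation period (date of examination on or after Day 28 after the completion of administration or date of discontinuation"), and 8.3.9 ties the end-date symptom and severity entry to the same examination, with no upper limit on its date. For patients whose observation stops before Day 28, 8.3.9 says "the highest severity by that point and the severity as of the date of discontinuation of the observation period should be recorded". Under effectiveness analysis, Protocol 8.7 states that "the number of patients by severity on the end date of the observation period will be tabulated".

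SAP 6.2 says that "the primary definition of the end date will be up to Day 28 after the end of treatment", and Table 2 in SAP 10.2 repeats it: "Primary definition: Up to Day 28 after the end of treatment". No lower bound is given. Table 2 adds two secondary definitions: up to 42 days, and the entire period. SAP 7 treats a value outside its acceptable window as missing and does not impute it. SAP 8.2.4 plans the secondary definitions as sensitivity analyses and excludes subgroup analyses from them. SAP 8.2.4.7 nevertheless restricts the resolution and improvement subgroup analyses to the entire period.

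**The concern.** The primary window stops on the day when the protocol's completer examination becomes possible. Taken literally, the primary tables keep early discontinuers, whose evaluation precedes Day 28, and drop completers unless they were examined on Day 28 itself.

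The outcomes affected are symptoms and severity on the end date, resolution and improvement from the start of treatment, and resolution and improvement after worsening. Severity on the end date is one of the protocol's own effectiveness tabulations. Worsening, highest severity, death and hospitalization do not depend on this evaluation and are unaffected.

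Two further problems follow:

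- **Selection.** Whether a patient is evaluable depends on the examination date and on early stopping. The end statuses in Protocol 8.3.8 include improvement of symptoms and death, so selection can be related to outcome, in either direction.
- **Visibility.** For highest severity, SAP 6.2 gives a separate *unknown* label "if the date of the highest severity is the day after the end of the evaluation period or later". The end-date endpoint has no such label. Its *unknown* category is split only into symptoms unknown and symptoms not recorded, so the primary table cannot separate a late evaluation from one never made.

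**Working it through.** **Overlap of the windows.** The SAP primary window is day ≤ 28 after the end of treatment (SAP 6.2 and Table 2). The completer examination is day ≥ 28 (Protocol 8.3.8 and 8.3.9). The intersection is Day 28 alone. With the 42-day definition it is Days 28 to 42, which is 15 days. With the entire period it contains every completer examination.

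**From outside the window to unknown.** SAP 7 makes the value missing, the protocol collects no earlier end-date evaluation to replace it, and the endpoint categories in SAP 6.2 place missing entries under *unknown*. No sentence says this outright for end-date values, but SAP 6.2 applies the same logic explicitly to highest severity. Patients without symptoms at the start appear to keep that category for improvement whatever the end entry (Table 5), so for resolution and improvement from the start the loss falls on those symptomatic at the start.

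**Size.** The plan states no figure to reproduce. The inputs below are assumptions, not values from the documents:

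- p: share of completers examined exactly on Day 28. It is 1 if all are, and 1/2, 1/7 or 1/14 if examinations spread evenly over Days 28-29, 28-34 or 28-41.
- d: share discontinuing before Day 28, set at 10%.
- e: share of discontinuers with an end evaluation recorded, set at 100% or 50%.
- rc, rd: true resolution in completers and discontinuers. All patients are taken as symptomatic at start, and rc does not depend on examination day.

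Formulas:

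- Completers lost = 1 − p
- Evaluable = d·e + (1 − d)·p
- Discontinuers' share of evaluable patients: s = d·e / evaluable
- Error in resolved among patients with known status = (s − d)(rd − rc)

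Example, Days 28-34 with e = 100%: evaluable = 0.10 + 0.90/7 = 22.9%, unknown = 77.1%, s = 0.10/0.229 = 43.8%. With rc = 90% and rd = 60%, the error is (0.438 − 0.10)(0.60 − 0.90) = −10.1 points.

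| | All on Day 28 | Days 28-29 | Days 28-34 | Days 28-41 |
|---|---|---|---|---|
| Completers lost | 0% | 50.0% | 85.7% | 92.9% |
| Unknown, e = 100% | 0% | 45.0% | 77.1% | 83.6% |
| Unknown, e = 50% | 5.0% | 50.0% | 82.1% | 88.6% |
| s, e = 100% | 10.0% | 18.2% | 43.8% | 60.9% |
| s, e = 50% | 5.3% | 10.0% | 28.0% | 43.8% |
| Error, rd = 60%, e = 100% | 0.0 | −2.5 | −10.1 | −15.3 |
| Error, rd = 60%, e = 50% | +1.4 | 0.0 | −5.4 | −10.1 |
| Error, rd = 95%, e = 100% | 0.0 | +0.4 | +1.7 | +2.5 |

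Errors are in percentage points with rc = 90%. The true overall value is 0.10 × 60% + 0.90 × 90% = 87.0% when rd = 60%, and 90.5% when rd = 95%.

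**On the planned denominator.** SAP 8.2.4.3 tabulates the proportion in each category, with *unknown* as one of them. Resolved then reads d·e·rd + (1 − d)·p·rc. For rd = 60% and e = 100% this is 87.0%, 46.5%, 17.6% and 11.8% across the four columns, against a true 87.0%.

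**The case against.** The strongest reply is that the SAP largely deals with this already. The 42-day and entire-period tables are planned, no data are lost, and the entire-period table delivers the protocol's tabulation. Comparing *unknown* counts between the Day 28 and entire-period tables would show how many patients the window cost. The entire-period overall table also gives a like-for-like comparator for the subgroup results. The study is exploratory, with no significance level or decision rule, so little hangs on which table is called primary. Day 28 has a basis in the protocol, because the observation period ends there. Any wider window admits evaluations outside that period.

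The size is also unproven. Protocol 8.2.3.1 asks for "Sites where patients can be followed up at the time of the site visit or by telephone, home visit, etc" as a site condition, so examination on Day 28 is feasible and a loss of zero cannot be excluded. A higher discontinuation rate would shrink the *unknown* share: at d = 50% and e = 100% it is 0.5 × (1 − p), or 25%, 43% and 46% for the three spreads. The errors among patients with known status use a denominator the SAP does not plan; in the planned table the loss appears as a visible row.

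All of this stands as a limit on the consequences. It does not remove the mismatch. The table labelled primary still excludes most of the examinations the protocol allows for completers, and the reader depends on sensitivity analyses to obtain the protocol's own result.

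**Conclusion.** The concern holds. That the two windows meet only on Day 28 is exact. That later examinations become *unknown* follows from SAP 7 read with the endpoint categories, supported by the explicit parallel rule for highest severity. The effect ranges from no completers lost to 93% lost under the visit spreads assumed, and the documents give no visit timing to narrow this. Bias among evaluable patients can go either way and vanishes if nobody discontinues early, in which case only the *unknown* share remains. The consequence is for description only, is confined to the end-date outcomes, and is softened by the planned wider-window tables. It should be fixed, but it does not threaten the study's other results.

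**What to change.** For the end-date endpoints, make one of the wider windows in Table 2 primary, either up to 42 days or the entire period, and keep the Day 28 window as the sensitivity analysis. Use the same window for the overall tables and the resolution and improvement subgroup tables, and reconcile SAP 8.2.4 with SAP 8.2.4.7 on which window subgroups use. Add an *unknown* sub-label for evaluations recorded after the window, modelled on the one for highest severity, so that the number lost to the window is shown.

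No new data are needed, and the overall runs are already planned. The work is one derived flag and revised table shells. Choosing the entire period leaves the resolution and improvement subgroup tables as they are but sets no upper limit on the evaluation date. Choosing 42 days sets a limit but requires those subgroup tables to be rerun. Either way, evaluation dates vary more between patients and some fall outside the 28-day observation period. The revision history gives the study status as completed at SAP Version 5, so this should be a dated revision, labelled as a late change, with the Day 28 result still reported.
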